3.1.2. Dose limiting toxicity (DLT)

A dose limiting toxicity (DLT) is defined as a grade 3 or higher adverse event as defined by the Common Terminology Criteria for Adverse Events (CTC-AE V5.0) considered by a safety review board as probably or definitely related to study treatment.

If more than 2 DLTs occur in the first 12 treated patients for at least 14 days, then the enrolment of additional patients in the treatment group will be stopped, otherwise the enrolment of planned patients will be confirmed.

In addition, in case of a life threatening (grade 4) adverse reaction enrolment in the treatment group, all treatment of ongoing patients will be immediately discontinued.

In both cases, enrolment will only be resumed upon the decision of the sponsor if the Data Safety Monitoring Board can conclude that the causality of the event was unrelated or unlikely related to study treatment.

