7.5. Recording AEs and SAEs

Severity of AEs will be assessed according to CTC-AE Classification Version 5.0.

Patients will be asked to report all AEs as part of the procedures performed at each study visit. The site personnel will document all AEs in the patient's medical record. All AEs subsequently must be recorded in the appropriate eCRF sections.

The following points must be recorded for each event:

- A description of the event in medical terms, not as reported by the patient;
- Date of onset (start date);
- Date of resolution (stop date);
- The time of onset with respect to administering the investigational product;
- The severity of the sign/symptom or clinically significant abnormal laboratory value according to CTC-AE Classification Version 5.0;
- The causal relationship between the investigational product and the occurrence of each AE. This will be assessed by each investigator using clinical judgment. Alternative causes, such as natural history of the underlying diseases, concomitant medications, other risk factors and the temporal relationship of the event to the investigational product will have to be considered. The causality of all AEs should be assessed by the investigator with the following question: Is there a reasonable possibility that the AE may have been caused by the investigational product? And answered "NO" (if not related) and "YES" (if related);
- Action taken regarding the investigational product:
 - No action;
 - Temporary discontinuation;
 - Permanent discontinuation;
 - Patient's outcome:
 - Recovered without sequelae / resolved without sequelae;
 - Recovered with sequelae / resolved with sequelae;
 - Recovering/Resolving;
 - On-going;
 - Fatal (for SAEs only).

If in any one patient, the same AE occurs on several occasions, the AE in question must be documented and assessed a new each time.

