7.6. Reporting of SAEs to ABIVAX or its designee

Throughout the study, the reporting of SAEs to the Sponsor or its designee will be done through the SAE forms.

It is the investigator's responsibility to ensure that the SAE report is submitted to IntuVigilance Limited **within 24 hours after knowledge of the event(s)**.

The study specific SAE form should be completed as thoroughly as possible, with all the available details of the event and signed by the investigator or designee. The investigator will assess causality between

the study drug and the adverse event (AE) / serious adverse event (SAE) according to the table outlined below:

Related	A clinical event, including laboratory test abnormality, occurs in a plausible time relationship to treatment administration, and which concurrent disease or other drugs or chemicals cannot explain.
Probably related	A clinical event, including laboratory test abnormality, with a reasonable time sequence to administration of the treatment, unlikely to be attributed to concurrent disease or other drugs or chemicals.
Possibly related	A clinical event, including laboratory test abnormality, with a reasonable time sequence to administration of the treatment, but which could also be explained by concurrent disease or other drugs or chemicals.
Unlikely to be related	A clinical event, including laboratory test abnormality, with a temporal relationship to treatment administration which makes a causal relationship improbable, and in which other drugs, chemicals or underlying disease provide plausible explanations.
Unrelated	A clinical event, including laboratory test abnormality, with little or no temporal relationship with treatment administration. Typically explained by extraneous factors (e.g., concomitant disease, environmental factors or other drugs or chemicals).

An assessment of causality should always be provided at the time of the initial report. If the investigator or designee does not have all information regarding the SAE, he/she should not wait to receive additional information before completing the form and notifying IntuVigilance Limited.

Additional or follow-up information relating to the initial SAE report, will be requested, if necessary. Again, this information is to be completed and submitted through the SAE forms within 24 hours of receipt of the information.

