8.4. Safety Analyses

Adverse events will be coded using the standard dictionary (MedDRA) down to the lower level term (LLT).

An overall summary table will be presented (Any adverse event, any treatment emergent adverse event (TEAE), any serious adverse event (SAE), death, any grade 3 or higher adverse events from baseline to the end of Study. This analysis will be conducted on SAF population.

Two periods will be defined for TEAE:

- Any adverse event which occurs or worsens from first dosing to Day 84;
- Any adverse event which occurs after Day 84.

Adverse events will be described by primary system organ class and preferred term. Numbers and percentage of patients, and number of occurrences of adverse event will be presented for:

- TEAE;
- Serious TEAE;
- TEAE leading to drug discontinuation;
- TEAE of grade 3 or 4;
- TEAE for which relationship with the study drug is recorded as possible or probable.

Analysis of safety will be performed on the safety data set consisting all subjects who received at least one dose of ABX464 in the study.

Primary safety endpoint, the rate of all treatment emergent adverse experiences, will be compared in subjects who received a given dose of ABX464 or placebo by likelihood ratio chi-square test on a 10% two-sided significance level.

Further assessment of safety will be based on the frequency of adverse events (with and without regard to causality) graded according to the CTC-AE Classification and also, the review of individual values for clinical laboratory data, vital signs and ECG focusing on the detection of abnormal values and PCSAs [potentially clinically significant abnormalities (PCSAs) determined upon investigator considerations].

Adverse events will be tabulated (counts and percentages) by group. All adverse events will be listed, and the data will be tabulated by body system/organ class. Adverse event tabulations will include all treatment emergent adverse events, which will be further classified by severity, and relationship to treatment and dose level.

Clinical laboratory parameters, vital signs, ECG will be summarized by using descriptive statistics (n, mean, SD, SEM, median, minimum and maximum). Number of patients with at least one abnormal value will be tabulated (counts and percentages) for each parameter in summary shift tables, by group and dose.

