Events will be classified as treatment-emergent if they started or increased in severity on or after the first date and time of medication dosing at Visit 1 and up to study closure or withdrawal date. If an event start date is partial, then the start day, month, year or stop date will be used to determine if the event is treatment-emergent. If the classification of the AE cannot be determined from the data available, then the event will be considered treatment-emergent.

Treatment-emergent adverse events (TEAEs) will be further classified as follows:

Severe TEAEs: Severity classified as 'severe' (Common Toxicity Criteria [CTC] grade 3 or 4) or missing.

Serious TEAEs: Serious classified as 'yes' or missing.

Drug-related TEAEs: Relationship to study drug classified as 'related' or missing.

Serious drug-related TEAEs: Both serious and drug-related, as specified above.

TEAEs leading to withdrawal from study: Action taken classified as 'discontinued'.

All AE summary tables will show the number (%) of patients having at least one event and the number of events in each treatment group and overall. Median duration of AEs (from baseline to occurrence) will be presented in the tables. Note: If a patient has multiple AEs with the same preferred term, these will be summarised once within the count for N (%) of patients, but each event will be counted within the number of reports n of each AE. Changes in severity of the same AE (if collected) will be counted only once within the number of reports n of each AE.

The following will be presented in listing format within the data summaries:

- Deaths (Table 14.3.2.1);

- Serious Adverse Events (*Table 14.3.2.2*);
- Adverse Events which Led to Withdrawal (*Table 14.3.2.3*).

All adverse events (including non-treatment-emergent events) recorded on the CRF will be listed within the data listings.

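### Drug-related TEAEs: Protocol 8.4 omits the strongest causality grade and fits no YES/NO record, and the SAP redefines the category and drops its table without saying so

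*Protocol*

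**What the plan says.** **Recording.** Protocol 7.5 asks for the causality of every AE through one question, "Is there a reasonable possibility that the AE may have been caused by the investigational product", answered NO or YES. Protocol 7.6, in the section on SAE reporting, asks the investigator to assess causality between "the study drug and the adverse event (AE) / serious adverse event (SAE) according to the table outlined below". That table has five levels: Related, Probably related, Possibly related, Unlikely to be related, Unrelated. Related is the top level, for an event that "occurs in a plausible time relationship to treatment administration, and which concurrent disease or other drugs or chemicals cannot explain".

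**Analysis, protocol.** Protocol 8.4 lists five TEAE presentations by SOC and PT. The fifth is "TEAE for which relationship with the study drug is recorded as possible or probable".

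**Analysis, SAP.** SAP 11.6.1 defines "Drug-related TEAEs: Relationship to study drug classified as 'related' or missing", and a serious drug-related category built on it. Its own list of TEAE presentations has four items and stops at grade 3 or 4. SAP 14.1 contains no drug-related TEAE table. SAP 1.2, on changes from the protocol, mentions only the efficacy sets.

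**DLT rule.** Protocol 3.1.2 and SAP 7 both refer to an event "considered by a safety review board as probably or definitely related to study treatment".

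**The concern.** Safety is the primary objective, and AEs split by causality are a listed secondary endpoint (Protocol 2.4, SAP 4.2.2). A programmer following Protocol 8.4 literally would leave the most clearly attributed events out of the drug-related table, or would have an empty table if the database holds only YES/NO. A programmer following the SAP would use another definition and would have no table to produce. If this is still open at unblinding, the definition of drug-related would be chosen with the treatment codes known.

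**Working it through.** No power, alpha or rate figure is involved, so the check sets the categories side by side. Each row is a value that the protocol allows to be recorded. The entries show whether each analysis rule selects it when labels are taken literally.

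| Recorded value | Protocol 8.4 (possible or probable) | SAP 11.6.1 (related or missing) |
|---|---|---|
| 7.6 Related | no | yes |
| 7.6 Probably related | yes | not by label |
| 7.6 Possibly related | yes | not by label |
| 7.6 Unlikely to be related | no | no |
| 7.6 Unrelated | no | no |
| 7.5 YES | no matching term | yes |
| 7.5 NO | no | no |
| Missing | no rule given | yes |

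**Step 1: Protocol 8.4 on the five-level scale.** Three grades express at least possible causation. The rule takes two of the three, and the one left out is the strongest.

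**Step 2: Protocol 8.4 on the YES/NO scale.** Neither of the two answers is called possible or probable, so the rule selects no event.

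**Step 3: which scale the SAP means.** The shells for Table 14.3.2.2 (SAEs) and Listing 16.2.7 (all AEs) show relationship to study drug as Yes/No. SAP 9.2.1 schedules no external data transfers, and SAP 9.2.2 says there is no other non-CRF data. The SAP's word related therefore most naturally means YES in Protocol 7.5. That is an inference, because no document states it. It also raises the possibility that the five-level grades will not be in the analysis data at all.

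**Step 4: how far the two definitions agree.** With five-level labels read literally, they share no category. If YES is assumed to cover Related, Probably related and Possibly related, the SAP set contains the whole protocol set and adds the events graded Related and those with causality missing. Agreement therefore runs from none to full containment, depending on a mapping that is not written down.

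**Step 5: what the SAP would output.** Four of the protocol's five items have tables, one for each of two periods (Tables 14.3.1.2.2 to 14.3.1.5.2). The related item has none, and the overall AE summary shell (Table 14.3.1.1) has no related row. The drug-related and serious drug-related categories are defined but no listed table uses them.

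**The case against.** The strongest reply is that the SAP is workable as it stands. On the YES/NO reading, its rule is coherent, handles missing values and would count possible and probable events. A reader might infer from the labels that the protocol and SAP definitions are disjoint. The documents do not support that as a finding: it requires applying the SAP's word to the five-level table, and the SAP's own shells point to Yes/No.

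Two further points limit the harm. Protocol 8.4 and SAP 11.6.1 both say that TEAE tabulations will also be classified by relationship, and Listing 16.2.7 shows each event with its relationship. An event graded Related would therefore be missing from one table, not from safety reporting. Also, the test on the primary safety endpoint uses all TEAEs regardless of cause.

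These points stand, and they limit the consequence. They do not repair Protocol 8.4, which fails on either scale. Nor do they supply the missing table: the general sentence on relationship is retained in the SAP, but no table or shell is allotted to it.

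The DLT wording could also be read as a third, conflicting definition of drug-related TEAEs. It is not one. It describes a safety board's judgement for an enrolment decision, SAP 7 leaves the evaluation process to the DSMB Charter, and the rule shares the grade probably with Protocol 8.4. Nor can it be said that no case report form offers a definite grade, because the forms are not reproduced. Finally, it cannot be said that non-serious AEs carry only YES/NO, since the text of Protocol 7.6 names both AEs and SAEs.

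**Conclusion.** The defect is real and limited. Two causality scales are used without a mapping. Protocol 8.4 excludes the top grade on one and selects nothing on the other. The SAP changes the definition, omits the corresponding table and does not declare either change. Steps 1, 2 and 5 rest on the text alone. The reading of the SAP as YES or missing rests on its listing shells, and containment of the protocol set further assumes that YES covers all three upper grades.

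The effect is on descriptive secondary safety tables. The number of events affected cannot be estimated, because the documents give no expected distribution of causality grades. The primary endpoint and its comparison do not change.

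As a side note, the DLT rule uses definitely, a term on neither protocol scale. Protocol 3.1.2 and SAP 7 must be reconciled with Protocol 7.5 and 7.6. No view is taken here on the causality threshold.

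**What to change.** 1. In Protocol 8.4 and SAP 11.6.1, use one definition: a TEAE is drug-related if the 7.5 question is answered YES or, where only the five-level scale is recorded, if it is graded Related, Probably related or Possibly related. Missing causality counts as related, as the SAP already provides. This also settles which record governs when both exist.
2. Add a drug-related TEAE table by SOC and PT to SAP 14.1. The existing shell for Table 14.3.1.2.2 serves. If it follows the other four items, there is one table for each period.
3. Record the change of definition in SAP 1.2.
4. Reconcile the DLT causality wording with the recorded categories, as noted above.

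The cost is one definition, one table in an existing layout and one line in SAP 1.2. No new data are collected. It should be done before the treatment codes are opened, the point by which SAP 1.1 already requires the plan to be final.

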8.5. Clinical laboratory evaluation

Descriptive statistics for laboratory parameters will be computed at each scheduled assessment. If relevant for some parameter, change from baseline will also be tabulated.

In addition, shift tables from baseline will be presented.

8.6. Determination of sample size

The primary efficacy endpoint is the rate of subjects meeting the ACR20. This response rate will be compared in subjects who received a given dose of ABX464 or placebo by likelihood ratio chi-square

test. The result of the test will be interpreted in a descriptive manner therefore no adjustment for multiple comparison is applied.

For the sample size assessment, the following assumptions will be made:

- Response rate (ABX464): 0.65
- Response rate (placebo): 0.25

According to literature the ACR20 response rate for ABX464 + MTX treated subjects is expected to be between 50% and 65% while that in the placebo + MTX group is assumed to be approximately 25 to 30% (Xeljanz® Summary of Product Characteristics; ORAL Standard Investigators - N Engl J Med 2012; 367:508-519 August 9, 2012 (8)).

- Type 1 error: 10% two-sided
- Group allocation rate (ABX464 / placebo): 1:1:1

If the above assumptions and definitions hold true with a sample size of 60 subjects receiving two doses of ABX464 or placebo in a ratio of 1:1:1 the study has 84% power to show a difference in response rate between one active study group and placebo.

Subjects who terminates the study prematurely will be considered failures therefore no adjustment for drop-outs is needed.

Primary safety endpoint is the rate of all treatment emergent adverse experiences. The above sample size is sufficient to detect an increase in general treatment emergent adverse experience rate from 10% to 50% with 89% power by likelihood ratio chi-square test on a 10%, two-sided significance level.

If approximately 20 subjects receive ABX464 the study has 88% chance to detect at least 1 specific treatment emergent AE if the underlying rate of occurrence is 1:10.

When the underlying rate of occurrence is around 1:20 the sample size of 40 subjects receiving active treatment is sufficient to observe at least 1 such an event with a probability of 87% in the active treatment group.

9. STUDY CONDUCT CONSIDERATION

9.1. Regulatory and Ethical Considerations

9.1.1. General Requirements

The study will be conducted in compliance with the study protocol, ABIVAX / SIMBEC ORION Standard Operating Procedures and in accordance with any local regulatory requirements, to ensure adherence to Good Clinical Practice (GCP) as described in the following documents:

- ICH Harmonized Tripartite Guidelines for Good Clinical Practice (ICH E6 (R2)).
- US 21 Code of Federal Regulations dealing with clinical studies (including parts 50 and 56 concerning informed consent and IRB regulations).
- Directive 2001/20/EC on the approximation of the laws, regulations and administrative provisions of the Member States relating to the implementation of good clinical practice in the conduct of clinical studies on medicinal products for human use and its guidance.
- Declaration of Helsinki and its amendments.
- EudraLex GMP guidelines Annex 13 related to shipment, storage and handling of investigational products.

Upon signing the protocol, the investigator agrees to adhere to the instructions and procedures described in it and thereby to adhere to the principles of Good Clinical Practice that it conforms to.

Written informed consents will be obtained for each patient before he or she can participate in the study.

ABIVAX will obtain favorable opinion/approval to conduct the study from the appropriate regulatory agencies in accordance with any applicable country-specific regulatory requirements prior to a site initiating the study in that country.

9.1.2. Independent Ethics Committee/Institutional Review Board

Prior to the start of the study, the study protocol and amendments if applicable as well as other appropriate study-related documents will be submitted to an independent Institutional Review Board (IRB) or independent Ethics Committee (IEC), respectively.

For each center it will be individually specified, who (investigator or sponsor) will be responsible for informing the IRB or IEC, respectively of any protocol amendments or new relevant information that require an ethical reconsideration of the study protocol.

If the investigator is responsible for obtaining approval, he/she should also obtain a statement from the IRB or IEC, respectively that it is organized and operates according to GCP and applicable laws and regulations.

9.1.3. Patient Informed Consent

It is the responsibility of the investigator to give each patient full and adequate verbal and written information regarding the aims, methods, anticipated benefits and potential hazards. The patient must be informed that participation is voluntary, and that they are free to withdraw from the study at any time without any disadvantages for their subsequent care. Although a patient is not obliged to give her/his reason(s) for withdrawing prematurely from the trial, the investigator should make a reasonable effort to ascertain the reason(s), while fully respecting the patient's rights. Written consent (signed and dated by the patient and the investigator) must be obtained prior to admission. The patient must be provided with a copy of the patient information and informed consent.

The data collected in this study will be processed anonymously at ABIVAX. Patients should be informed about the purpose of the planned computer data processing and the publication of the data (e.g. at scientific meetings). The patient must give consent to the computer processing and to the publishing of anonymous data.

The patient must be informed of and consent in writing that personal data relating to the trial may be patient to audits by Health Authorities and the sponsor. However, personal data will be kept strictly confidential and will not be made publicly available.

9.1.4. Compensation to Patients

Insurance coverage will be provided for all patients enrolled in the study from the time of the patient's inclusion in the study (i.e. date of signing the ICF). The insurance coverage will be provided by the Sponsor and will be in line with GCP guidance and legal requirements, but also in accordance with local regulations. A confirmation of insurance and corresponding insurance conditions should be archived in the Investigator File.

Besides, due to the cumbersome procedures related to the study (number of visits, pharmacokinetics samples) patients could be financially compensated by the Sponsor in accordance with the national regulations and the approval of the Ethics Committees.

